### 5.0 Designs and methodology

**Study Design:** This will be a hybrid 1 study design (mixed methods), where we are testing effects of a clinical intervention on relevant outcomes while observing and gathering information on implementation. We propose a matched cluster randomized controlled trial (2 arms, 6 clusters/arm, n=75 participants per cluster), using mixed methods. We will enroll PMTCT clients at Kenyan health facilities offering either HITSystem 2.1 intervention or standard of care (SOC) services to evaluate the efficacy, implementation, and cost-effectiveness of HITSystem 2.1 to increase complete PMTCT retention and viral suppression. Participants will be enrolled in PMTCT and followed through 6 months postpartum, with focused data collection at enrollment, delivery, and 6 months postpartum, Figure 1.

**(a) Study sites:** Study sites will be located in Siaya, Mombasa, and Kilifi Counties. These counties were selected due to their (1) elevated MTCT rates and (2) lower density of interventions targeting MTCT that could confound the results of this evaluation. To be eligible for selection and matching in the study, health facilities must (1) provide PMTCT, EID, and ART services and (2) not be involved in any ongoing PMTCT or EID interventions or research studies.

We will collaborate closely with the national PMTCT technical working group to facilitate strategic site selection to maximize the similarity of facilities matched on geographic region, patient volume, and HIV prevalence. Finalized matches are outlined in Table 2.

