### **(c) Sampling**

All HIV-positive pregnant women who present for care at study hospitals will be eligible for enrollment in the study. All eligible study candidates will be informed of the purpose of the research, including potential benefits and risks, prior to a request for written informed consent (Appendices 2A and 2B, see detailed informed consent section below). Women opting out of the study at intervention sites will have the option to either (1) access standard PMTCT services without enrollment in HITSystem 2.1, or (2) access HITSystem 2.1-supported PMTCT without their data being included in study analyses. Women opting out of the study at control sites will receive standard PMTCT services with their data being excluded from study analyses. Mentor mothers will document study enrollment and enrollment refusal at all sites.

Providers participating in interviews will be purposively sampled to represent a range of clinical departments and roles involved in the provision of PMTCT services.

**Sample size determination for Objective 1:** We estimated current levels of retention in complete, guideline-adherent PMTCT services based on findings from our R34 grant. Findings from our retrospective review at 4 Kenyan health facilities indicate only 50/424 (11.8%) of women enrolled in PMTCT received guideline adherent viral load testing. Based on average percentage point increases in complete retention achieved in previous studies (33% HITSytem 2.0 pilot [R34], 25% HITSytem 1.0 [R01]), we conservatively anticipate HITSytem 2.1 supported VL testing will exceed that of SOC by at least 20 percentage points (Table 3). We assume that the small subset of participants with guideline-adherent VL testing will be included among the larger population of those receiving complete PMTCT retention. To account for increased familiarity with guidelines over time and continually improving SOC, we assessed statistical power for contingencies with SOC guideline adherence as high as 18% using R package *clusterPower*. Assuming ICC=.05, the planned sample size of six 75-person clusters per arm provides 85% power to detect differences even smaller than the expected 20-percentage point difference across a range of possible SOC completion rates (Table 4). Using HITSytem 2.0 pilot data, we predict 28% attrition; thus, we need to enroll **n=96 women per cluster** (75 + 21).

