**Sample size considerations for Objective 2.** We draw upon limited pilot data, given the dearth of published data describing VL among women in pregnancy and in the postpartum periods, or estimates of VL of women who have disengaged from care in either period. Among PMTCT clients who received at least one VL test result, 31.3% of women in the control site had a detectable VL. Albeit small numbers, in the R34 intervention site which received intensified PMTCT retention support, but no prompts for VL testing or clinical action, 2/22 (9.1%) women had a detectable VL >1,000. These proportions reflect women engaged in clinical care during the study period. We estimate that women LTFU will have at least a 50% increased risk of a detectable VL given likely treatment interruption. In the control site, 24% of women were LTFU by the time of delivery, thus when averaging estimates for all women (retained and LTFU) we estimate 35% of women enrolled in SOC PMTCT will have a detectable VL compared to 10.2% (rounded up to 11%) in the HITSytem 2.1 sites (Table 5). With the strengthened VL component of HITSytem 2.1, we believe this estimate of 11% or less is realistic for the intervention arm. Using the R package *clusterPower*, we estimated power to detect a difference in proportions of detectable VL of .35 and .11. In an effort to demonstrate superiority of HITSytem 2.1 before accrual is complete, we will carry out an interim analysis after accruing 67% of the planned sample size in each arm. Splitting  $\alpha$  evenly between this interim analysis and the final analysis to preserve the overall  $\alpha$ -level at .05, power to detect the hypothesized .35 vs. .11 difference in the interim analysis at  $\alpha=.025$  is 95%. For a smaller difference of .30 vs. .11, power is 83% for the interim. Including the final analysis provides additional power. With the same estimates for attrition as detailed in Objective 1, the same number of participants are required for Objectives 1 & 2 (n= 75/cluster). However, a national stockout of viral load and infant HIV testing reagents caused a significant number of our sample to miss viral load and EID testing required for our aim 2 analyses. We have developed procedures to support postpartum VL testing and infant EID testing for the study (see below), however, prior to establishing these protocols, a total of 198 women and 320 infants missed routine testing due to this shortage. Two sites have already stopped enrolling, since they have met their required sample size of n=96 per site. We seek to add a total of n=30 participants to the ten sites that are still enrolling – for a total of n=300 participants across the study - to offset the statistical power lost due to missed testing from the national shortage. This would bring our total enrolled sample to n=1,452. We would enroll this sample for both aims 1 and 2, since both aims use the same patient population.

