## 7.0 Timeframe/duration of the study

We anticipate the study will last for five years, including a 6-8 month start up period for site selection and matching, IRB approvals, hiring and training, followed by a 1.5-year period to accrue the sample size of n=96 eligible women per site.

This 1.5-year accrual period will allow lower volume facilities (i.e. those with 4-5 HIV-positive pregnant women enrolling per month) to achieve the sample size. If a site fails to reach n=96 participants after 18 months, enrollment will be extended and the “maintenance monitoring” period at that facility will be shortened to achieve the target sample size. Prospective follow-up of all mother-infant pairs (pregnancy through postpartum) and provider interviews will require an additional year, after enrollment stops. Data cleaning and analyses will begin midway through Year 4, with dissemination at end of Year 5, see Table 9.

Table 9. Study Timeline

|                              | Year 1 |   |   |   | Year 2 |   |   |   | Year 3 |   |   |   | Year 4 |   |   |   | Year 5 |   |   |   |
|------------------------------|--------|---|---|---|--------|---|---|---|--------|---|---|---|--------|---|---|---|--------|---|---|---|
| Quarters                     | 1      | 2 | 3 | 4 | 1      | 2 | 3 | 4 | 1      | 2 | 3 | 4 | 1      | 2 | 3 | 4 | 1      | 2 | 3 | 4 |
| Study start-up               |        |   |   |   |        |   |   |   |        |   |   |   |        |   |   |   |        |   |   |   |
| Enrollment, sample accrual,  |        |   |   |   |        |   |   |   |        |   |   |   |        |   |   |   |        |   |   |   |
| Follow sample through 6m pp, |        |   |   |   |        |   |   |   |        |   |   |   |        |   |   |   |        |   |   |   |
| Maintenance monitoring       |        |   |   |   |        |   |   |   |        |   |   |   |        |   |   |   |        |   |   |   |
| Data cleaning and analyses   |        |   |   |   |        |   |   |   |        |   |   |   |        |   |   |   |        |   |   |   |
| Dissemination with partners  |        |   |   |   |        |   |   |   |        |   |   |   |        |   |   |   |        |   |   |   |

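### The enrolment target of 96 per cluster adds 28% to 75 instead of dividing by 0.72, so at 28% loss it yields about 69 women and not 75; the effect on power is small

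*Combined protocol and SAP*

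**What the plan says.** Section 5.0 describes the design as "2 arms, 6 clusters/arm, n=75 participants per cluster". Section 5.0(c) Sampling, under Objective 1, gives the basis for power: "Assuming ICC=.05", "the planned sample size of six 75-person clusters per arm provides 85% power". It then allows for loss: "Using HITSytem 2.0 pilot data, we predict 28% attrition; thus, we need to enroll" "n=96 women per cluster", with 75 + 21 shown in brackets.

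Under Objective 2 the same attrition is applied and "the same number of participants are required for Objectives 1 & 2 (n= 75/cluster". The powers quoted there (95% for .35 vs .11, 83% for .30 vs .11) are for an interim analysis at 67% of the planned sample, at α = .025.

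The same part of the section reports that two sites have stopped enrolling because they reached 96. It seeks 30 more women at each of the other ten sites, for a total of 1,452, to offset testing missed in a national reagent stockout (198 women). Section 7.0 repeats the target: "followed by a 1.5-year period to accrue the sample size of n=96 eligible women per site".

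**The concern.** The allowance of 21 is 28% of the number to be retained. Loss is a fraction of the number enrolled, so the retained number should be divided by 1 − 0.28. Multiplying by 1.28 always falls short; here 96 delivers 75 only if loss is at most 1 − 75/96 = 21.9%, which is below the plan's own 28%.

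The figure was acted on. It set the accrual target for every site, two sites closed on reaching it, and 12 × 96 = 1,152 is the base to which the 300 extra women were added. At stake is whether the analysable sample is the one the stated powers assume, and whether a reader can tell from the plan how many analysable women each objective expects.

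**Working it through.** **Inputs from the plan:** 6 clusters per arm, 75 per cluster, ICC .05 and 28% attrition (section 5.0(c)); Table 4 rates; interim at 67% with α = .025; extension of 30 women at ten sites; 198 women with missed tests. **Assumed:** two-sided α = .05 for Objective 1, ICC .05 for Objective 2 as well, equal cluster sizes in the power formula, no gain from matching.

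**1. The target**
- The plan's figure: 75 × 1.28 = 96.0, reproduced exactly.
- Yield at 28% loss: 96 × 0.72 = 69.1 per cluster, or 829 in all against 900 (71 fewer, 7.8%).
- Number that retains 75: 75/0.72 = 104.2, so 105 per cluster and 12 × 105 = 1,260.

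**2. Effect on Table 4**

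Effective n per arm = 6m/[1 + (m − 1) × .05].
- m = 75: 450/4.70 = 95.7
- m = 69.1: 414.7/4.41 = 94.1

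Power = Φ{[Δ√n − 1.96√(2p̄(1 − p̄))]/√(p₁(1 − p₁) + p₂(1 − p₂))}. For .08 vs .24 at m = 75: (1.565 − 1.016)/0.506 = 1.085, so 86.1%.

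| SOC vs HITSystem | m = 75 | m = 69 |
|---|---|---|
| .08 vs .24 | 86.1% | 85.5% |
| .10 vs .27 | 86.3% | 85.7% |
| .12 vs .30 | 87.0% | 86.4% |
| .14 vs .32 | 84.7% | 84.1% |

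At m = 75 all four rows lie within 2 points of the stated 85%. The loss is about 0.6 point. An unpooled variance gives 85.8–88.0% at 75 and 85.2–87.5% at 69. A t reference with 10 df gives about 78–81% and 77–80%. The level depends on the method; the loss hardly does.

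**3. Effect at the interim (Objective 2)**

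67% of 75 is about 50 per cluster, and the plan's figures reproduce there with the unpooled formula: 95.4% and 82.9%. If the 67% is taken of 69, about 46 per cluster, they become 94.9% and 82.0%, a loss of 0.5 and 0.9 point. The pooled formula gives 94.3% and 81.2% against 93.8% and 80.2%.

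**4. After the extension**
- Enrolled: 10 × 126 + 2 × 96 = 1,452, mean 121 per cluster.
- At 28% loss: 126 × 0.72 = 90.7 at ten sites and 69.1 at two; 1,045 in all, mean 87.1.
- Effective n per arm if both closed sites fall in one arm: 4 × 90.7/5.49 + 2 × 69.1/4.41 = 97.5, above the planned 95.7.
- If all 198 women with missed tests are lost to Objective 2 on top of attrition: (1,045.4 − 198)/12 = 70.6 per cluster. If they are removed before attrition: (1,452 − 198) × 0.72/12 = 75.2.

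**The case against.** Four replies carry weight.

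- **The extension overtakes the shortfall.** At 1,452 enrolled and 28% loss, each arm carries more information than six clusters of 75, wherever the two closed sites fall. This stands, before stockout losses. But the plan justifies the 300 women by the stockout and not by attrition, so for Objective 2 they may be largely used up.
- **69 is not established for Objective 1.** Under the Objective 1 specific methods, women missing a service are coded 0, and the analysis drops only those with a documented reason such as transfer, pregnancy loss or death. A woman simply lost to follow-up stays in the denominator. The analysed number from 96 enrolled therefore lies between 69 and 96, and the plan does not split the 28%. This stands. It also means that 75 + 21 does not describe how attrition enters the Objective 1 analysis.
- **Objective 2 loss may be lower.** Women without a viral load test are tracked by phone and home visit, and the assumed rates .35 and .11 already average over women lost to follow-up. This stands too, and it is why a range is given.
- **Power hardly moves.** Correct. The loss is smaller than the spread between reasonable formulas.

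A reader might infer that the trial is underpowered, that the current plan leaves all clusters at 69, that the Objective 2 powers were computed at 75 per cluster, or that the interim will fall at 46. The documents support none of these. ICC .05 dominates, enrolment has been raised, the quoted Objective 2 powers match about 50 per cluster, and 46 arises only if the 67% is counted on women enrolled towards 96.

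**Conclusion.** The arithmetic error is real and needs none but the plan's own numbers: 96 is the wrong inflation of 75 for 28% loss of enrolled women, and 105 is the right one. It should be corrected because 96 was used as the accrual target, closed two sites and underlies the 1,452. The shortfall against the 96 target is about 6 women per cluster if all 28% drop out of the analysis. The cost in power is about 0.6 point in Table 4 and about 1 point or less at the interim.

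Under the extension only the two closed sites stay below 75 on the 28%-loss reading, with no net loss of information before the stockout. For Objective 2 the average may come back to about 71–75 per cluster if every missed test is lost. Whether those 198 women overlap with attrition, or were tested later, is not stated. The power figures are normal approximations under the assumptions listed; the settings of the plan's own simulation are not given, so the size of the loss is firmer than the levels.

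**What to change.** 1. In section 5.0(c), replace the 75 + 21 step. Either give 105 as the number that retains 75 at 28% loss, or keep 96 and state that it yields about 69 under that loss. Make the mentions of 96 under Objective 2 and in section 7.0 agree with the choice.
2. State the expected analysable number after the extension for each objective:
   - Objective 1: between about 91 at ten sites and 69 at two (28% loss) and full enrolment (126 and 96), because undocumented loss is coded 0 and retained.
   - Objective 2: about 71–75 per cluster on average if all 198 missed tests are lost, up to about 87 if none are.
3. Re-run the stated powers at those sizes with the plan's own clusterPower simulation, rather than entering figures from an approximation.
4. Say whether the 67% interim trigger counts enrolled or analysable women, and of which planned number.

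The cost is wording and a short simulation run. This point gives no reason to add enrolment, reopen the closed sites, or change any procedure or analysis.

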## Procedures and Data Management

**Staffing and responsibilities.** We will hire and train one full time mentor mother for each study hospital. Each mentor mother will be trained to conduct study procedures specific to the study arm allocation. At all sites, mentor mothers will assess eligibility, conduct informed consent procedures and surveys, and facilitate VL testing at the time of delivery and by 6 months postpartum if not retested prior. At sites implementing HITSystem 2.1, mentor mothers will be the primary persons to enter and routinely update patient data. Mentor mothers also will lead patient outreach and follow-up efforts (phone or texting via HITSystem 2.1) and coordinate with community health workers (CHW) for targeted physical tracking if needed for VL testing at research-specific time points. Site Coordinators will routinely visit each study hospital to provide supportive supervision to ensure adherence to study protocols.

**Description of procedure and data collection:** At sites implementing HITSystem 2.1, all patient-specific data including: infant and maternal demographics; women's phone number and patient tracing information; women's appointment attendance and ART medication refills/pill counts; infant's date of birth, birth weight, and gestational age at delivery; dates of maternal VL sample collection, test processing, results return, and notification; and maternal VL results will be entered directly into HITSystem 2.1. ART adherence will be measured by pill counts collected at each consultation via HITSystem 2.1. At SOC sites, all clinical and PMTCT service related data will be collected in the existing paper-based registries by health care providers as part of routine services. Because routine pill counts for ART adherence are well outside of SOC practice and could modify behaviors in the control arm, we will rely on pharmacy refill records and chart review for any provider notes related to adherence. During their monthly site visits, site coordinators will review hospital registries at SOC sites to document patients' PMTCT engagement in study logs.

**Participant surveys:** A brief enrollment survey will collect same demographic and clinical data at control sites (without HITSystem 2.1) in addition to patient-level data regarding PMTCT information, motivation, partner status and support, HIV disclosure, depression (modified Edinburgh postnatal scale), and risk of violence (both arms, Appendix 2A). Repeated surveys after delivery and 6m postpartum (for VL sample collection described in Objective 2, both arms) will include these same patient-level measures to assess any changes that may mediate or moderate intervention impact (Appendices 2B & 2C). Participants will be compensated 200 KES for completion of each survey.

**Facility assessment form** (Appendix 2D) will be completed at the beginning, mid-point and end of study implementation to assess average resource level, annual PMTCT volume, and PMTCT provider-patient ratios.

**Provider surveys:** At baseline and again at the end of the study period, providers in both arms will be asked to complete a short survey (Appendix 2E) assessing provider role/ department, level of experience, knowledge and motivation regarding current PMTCT guidelines, and barriers and facilitators to provision of complete PMTCT services. We estimate n=5 providers per site to complete the survey for a total of n=60 providers (n=30 intervention, n=30 control). Prior to completing the survey, providers will complete an informed consent (Appendix 2C). Providers will be compensated 500 KES for completion of each survey.

**Supportive Supervision Visits** will occur monthly at all sites. During these visits, Site Coordinators will provide technical assistance and retraining, review study materials (informed consent forms, surveys), and review data for completeness and accuracy. The monthly frequency of site visits approximates programmatic HITSystem 1.0 implementation support in Kenya.

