### Objective 1 specific methods:

**Evaluate the efficacy of HITSystem 2.1 to increase the proportion of womens who receive complete PMTCT services through 6 m postpartum, per Kenyan guidelines.**

**Objective 1 outcomes.** The primary outcome for Objective 1 is the proportion receiving "complete PMTCT," an aggregate measure incorporating the documented receipt of all

designated services across the 3 PMTCT phases: maternal ART initiation, antenatal appointment attendance, facility delivery, EID linkage by 7 weeks of age, maternal VL testing and clinical action per national

Table 6. Aim 1 primary outcome: Services required for "complete PMTCT"

| Antenatal  | Delivery                | Postpartum (through 6m)   |
|--|-------------------------|---|
| 

• ART initiation

• On-time appointment attendance

• VL testing per guidelines

• Clinical action upon detectable VL

 | Hospital-based delivery | 

• EID linkage by 7 weeks

• VL testing per guidelines

• Clinical action upon detectable VL

 |

guidelines through 6 months postpartum (Table 6). Participants who receive all indicated services per guidelines will be coded as 1 or 'yes'. Participants missing  $\geq 1$  service will be coded as 0 or incomplete PMTCT services.

**Secondary outcomes** associated with Objective 1 will include gestational week at PMTCT enrollment, duration of PMTCT retention (weeks), and ART adherence (proportion >95%, proportion with missing/late prescription refill). Proportions will be calculated to describe each component of "complete PMTCT" separately (appointment attendance, VL monitoring, hospital delivery, EID linkage). Patient and facility-level factors will be assessed for their moderating impact on complete PMTCT. Provider characteristics will be aggregated and treated as facility-level variables. To assess pathways through which the HITSystem 2.1 works, we will measure provider and patient information and motivation as potential mediators

both pre- and post-intervention, and across study arms. Preterm births and infant weight at birth will be documented. We also will measure the proportion and timing/age of any HIV transmissions to infants, and maternal and/or infant deaths.

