test efficiency (turn-around time from sample to result, and turn-around time from result to patient notification), VL test utility (proportion of detectable VL results with clinical action per guidelines, such as: intensified adherence counseling and/or ARV regimen change), and repeated VL testing among those with detectable VL. We will document outcomes for pregnant and breastfeeding women who are LTFU to better enumerate outcomes for this population.

**Statistical analyses for Objective 2.** We will test for differences on binary outcomes between arms using logistic mixed models with adjustment for clustering and select covariates. After transformation (e.g., log) of turn-around time values if needed, differences in time will be assessed using appropriate generalized or linear mixed models. Post hoc analyses will assess person-level characteristics as moderators of the HITSystem 2.1 effect to assess whether the HITSystem 2.1 is more effective for specific subgroups. Any differences will guide future adaptations to improve efficacy among specific populations. The same methods described for mediation analysis of information and motivation will be applied in Objective 2.

Objective 3 specific methods:

**Evaluate the reach, effectiveness, adoption, implementation fidelity and maintenance (REAIM model) of HITSystem 2.1 using system data and surveys with providers and patients.**

We will evaluate the implementation of HITSystem 2.1 components to guide programmatic implementation and increase sustainable use in government health facilities. The RE-AIM framework is well suited to evaluate the implementation of system-level interventions, and outlines the public health impact as the intersection between: Reach, Effectiveness, Adoption, Implementation, and Maintenance, Table 6.

**Reach:** We will assess the proportion of eligible participants enrolled in HITSystem 2.1 at intervention sites by comparing HITSystem 2.1 enrollment with paper-based PMTCT registers. Reasons for non-participation will be documented for all eligible participants not included in the study. Among participants, data collected through the patient enrollment surveys will be used to describe characteristics of the sample and compared with national estimates to assess representativeness to national population of HIV+ pregnant women.

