#### 6.0 Data storage and management

All relevant clinical data at intervention sites will be captured through the HITSystem's online, automated system which produces output in Excel format. Patient specific information (including infant and mother demographics; mother's phone number and patient tracing information; PMTCT appointment attendance, maternal viral load testing and results, ART adherence, infant's date of birth; infant weight and gestational age at delivery; dates of sample collection, HIV test processing, results return, mother notification; and date of infant ART initiation for positive infants) will be entered by the Mentor Mother at the hospital during the first and subsequent PMTCT consultations to capture relevant demographic and clinical data and laboratory results. *Data will be de-identified* and maintained for each mother-infant pair within the password-protected HITSystem using a numeric ID to protect the identity of all participants. The site coordinators will routinely visit HITSystem sites for data quality assurance. At non-HITSystem sites, we will use individual patient (mother and infant) files, augmented by available hospital paper-based registers and the national laboratory online database to collect relevant routine clinical data. Patient records will be filled out by personnel performing the respective actions. The site coordinator will routinely visit non-HITSystem study sites to conduct retrospective record review of patient records and

enter relevant study data into a secured electronic database. As with HITSystem data, each mother-infant pair will be identified by a numeric study ID to protect their identity.

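### Service receipt and ART adherence are ascertained differently in the two arms, so a difference in recording could be read as an intervention effect

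*Combined protocol and SAP*

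**What the plan says.** **Intervention sites.** Under Procedures and Data Management, appointments, refills and pill counts, and viral load (VL) dates and results go straight into HITSystem 2.1, where "mentor mothers will be the primary persons to enter and routinely update patient data". The dashboard in Figure 1A lists patients whose services are delayed or whose status is missing, for example an unknown delivery status.

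**SOC sites.** The same section says: "At SOC sites, all clinical and PMTCT service related data will be collected in the existing paper-based registries by health care providers". At monthly visits, "site coordinators will review hospital registries at SOC sites to document patients' PMTCT engagement in study logs". Section 6.0 (Data storage and management) is broader: the source is the individual patient file, "augmented by available hospital paper-based registers and the national laboratory online database to collect relevant routine clinical data".

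**Primary outcome.** Objective 1 specific methods define complete PMTCT as "an aggregate measure incorporating the documented receipt of all" designated services. A woman with one or more services missing is coded 0. Table 6 has eight entries; the two on clinical action apply only after a detectable VL.

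**Adherence.** For intervention sites, "ART adherence will be measured by pill counts collected at each consultation via HITSystem 2.1". SOC sites use pharmacy refill records and provider notes, because introducing pill counts there might change behaviour. Two secondary adherence outcomes are listed: the proportion above 95%, and the proportion with a missing or late refill. Objective 4 uses optimal adherence as a secondary cost-effectiveness driver and uses adherence data to calculate wastage saved.

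**Analysis.** The Objective 1 analysis is a logistic mixed model with a random site intercept and selected covariates. It includes no validation of the records and no sensitivity analysis for differences in recording.

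**The concern.** The outcome is scored from the record, and no rule distinguishes a service that was not given from one that was given but not written down. The intervention includes prompts to complete the record, and these operate in one arm only. Because the outcome requires every service, small per-service gaps in recording compound. Such a gap is a systematic error, so enrolling more women or sites does not shrink it, and a random site intercept does not adjust for it.

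For adherence the problem is more direct. A proportion above 95% from pill counts and a classification from refill records or chart notes are two different measures. Their between-arm difference has no clear meaning, yet it can reach Objective 4.

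At stake are the interpretation of one of the two primary outcomes and one strand of the cost-effectiveness analysis.

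**Working it through.** **1. The plan's own power figure.** Inputs from Sampling and Table 4: six clusters of 75 per arm, ICC .05, 85% power. Two-sided alpha of .05 is my assumption, since none is stated for Objective 1.

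- Design effect = 1 + (75 − 1) × .05 = 4.7. Effective n per arm = 450 / 4.7 = 95.7.
- Power = Φ[(d − 1.96 × SE₀) / SE₁], where SE₀ uses the pooled rate and SE₁ the separate rates. For .12 vs .30: SE₀ = √(.21 × .79 × 2 / 95.7) = .0589; SE₁ = √((.12 × .88 + .30 × .70) / 95.7) = .0574; power = Φ[(.18 − .1154) / .0574] = 87.0%.
- The four rows of Table 4 give 86.1%, 86.3%, 87.0% and 84.7%. The stated 85% is reproduced.

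**2. Spurious gap when care is identical.** Let p be true completion in both arms and s the chance that a delivered service is recorded, with services independent. Six Table 6 entries are treated as applying to every woman. Then:

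- Observed rate = p × s⁶
- Spurious gap = p × (s_HITS⁶ − s_SOC⁶)

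The documents give no recording rates; 99%, 95% and 90% are assumptions. .99⁶ = .941, .95⁶ = .735, .90⁶ = .531, so the multipliers are .206 (99% vs 95%) and .410 (99% vs 90%).

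The chance of a false significant result favouring HITSystem is Φ(gap / SE − 1.96), with SE = √([a(1 − a) + b(1 − b)] / 95.7) for observed rates a and b. The nominal value is 2.5%. The figure in brackets is a beta-binomial simulation (20,000 trials, t-test on cluster proportions, 10 df). Both ignore the site matching.

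| True completion | Gap, 99% vs 95% | False win | Gap, 99% vs 90% | False win |
|---|---|---|---|---|
| .08 | 1.7 points | 7% (6%) | 3.3 points | 16% (14%) |
| .14 | 2.9 points | 9% (8%) | 5.7 points | 26% (23%) |
| .20 | 4.1 points | 12% (10%) | 8.2 points | 36% (32%) |
| .30 | 6.2 points | 17% (15%) | 12.3 points | 55% (47%) |

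The first two rows are the ends of the SOC range in Table 4. The planned minimum detectable differences there are 16 to 18 points.

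**3. How far the assumptions drive this.**

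- If only three services were exposed at 99% vs 95%, the multiplier is .99³ − .95³ = .970 − .857 = .113. The gap is 0.9 to 1.6 points at .08 to .14, and 2.3 to 3.4 at .20 to .30.
- If gaps in recording cluster within women, the gap falls. In the extreme where a woman's record is either wholly complete or not, the multiplier is .99 − .95 = .04, or 1.2 points at p = .30.
- If s is equal in both arms, the gap is 0 and the false-win rate returns to nominal (simulated 2.6% at p = .30).

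**4. Adherence.** No arithmetic is needed. The above-95% outcome has a pill count behind it in one arm only. Refills are captured in both arms, and a missing or late refill outcome is already specified.

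**The case against.** A reader might infer that SOC scoring depends on paper registers alone and that better documentation will therefore favour HITSystem. The documents do not support this. Section 6.0 adds patient files and the national laboratory database for SOC, which should protect VL and infant tests better than attendance or clinical action. Supervision visits check completeness monthly at all sites, and every hospital, SOC included, has a study-hired mentor mother. No recording rate appears for either arm. The opposite direction is also possible: SOC scoring draws on several sources, so a service noted only on paper at an intervention site could be the one that is missed.

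Some components also have a second route that is the same in both arms. The enrollment survey asks when treatment began, and the delivery survey asks where the woman delivered. The plan does not say that these score the outcome, but they make six equally exposed services a pessimistic model.

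On adherence, withholding pill counts at SOC sites is a reasoned choice and the outcome is secondary. Only the above-95% version is non-comparable. The primary cost-effectiveness driver is infant diagnosis at the first test, not adherence. For Objective 2, the delivery VL is study-coordinated and run by a research laboratory in both arms, so it is much less exposed, although the routine postpartum result still comes from the medical record.

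It is also tempting to rescore the primary outcome from paper sources in both arms. Objective 3 shows registers at intervention sites being used for "comparing HITSystem 2.1 enrollment with paper-based PMTCT registers". That does not show that they hold full service records. If electronic entry displaces paper, such a rescoring could bias against the intervention.

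These points limit the certainty, the size and the remedy. They do not give the arms a common source, and they do not supply an analysis that could detect a difference in recording.

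**Conclusion.** The concern stands as a risk of unknown size and direction. The sources differ by arm, an unrecorded service counts as not received, and the plan cannot tell recording from care. Under assumed recording of 99% vs 95% or 90% over six independent services, the spurious gap is about 2 to 6 points at the planned SOC rates of .08 to .14, and 4 to 12 points at .20 to .30. It is smaller if fewer services are exposed or if gaps cluster within women. At the planned rates this falls well short of the 16 to 18 points the trial is sized to detect, but it could inflate an estimate or help a marginal result reach significance. That HITSystem will be favoured is plausible from the missing-status alerts, but it is not shown.

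The non-comparability of the above-95% adherence measure depends on no assumption. No sample-size figure changes. Severity: SHOULD-FIX.

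**What to change.** 1. **Adherence.** Make the between-arm comparison, and the adherence input to Objective 4, on pharmacy refill records in both arms. Report the pill-count above-95% measure descriptively for the intervention arm only. This needs no new measurement, because refills are already captured in both arms and the refill outcome is already listed.

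2. **Complete PMTCT.** Keep the primary scoring. At their existing monthly visits, have the site coordinators re-abstract a random sample of women per site, in both arms, with one form and the same sources: patient files, registers and the national laboratory database. Estimate recording completeness by component and arm, and report a pre-specified sensitivity analysis of complete PMTCT on the common sources. Fix the sample size and the rule for conflicting sources before any comparison by arm.

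**Cost and limits.** The abstraction work is modest and must be done while records are accessible. Paper records at intervention sites may be less complete, so report both scorings and treat neither as the reference standard. Re-abstraction cannot find a service that was recorded nowhere.
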